# **Study population**

Our target population is healthy adults aged 16 to 35 years. This study is being conducted as part of a larger project examining the correlation of the orthoptic measures with symptoms of concussions; therefore, this population has been selected to match that target population of young adults with concussion symptoms to ensure applicability of findings to the patient population in our larger study. We will exclude participants who have conditions or are taking treatments that could affect the results of the orthoptic tests.

### Inclusion Criteria

- o Participants must be 18 years or older
- o Informed consent to participate in the study

### **Exclusion** Criteria

- o Participants with strabismus or a history of treated strabismus
- History of migraine or know neurologic disorders
- Use of myorelaxants, as they interfere with orthoptic testing
- We will exclude any participants who are currently taking medications for depression, anxiety or other psychological condition.

Although a random sample is usually the preferred sampling method, it is difficult to achieve in a timely manner and can be very costly [17]. Further, in the context of our study a random sample is not necessary because we are interested in examining the test-retest reliability across two measurements in the same participant. Therefore, we do not expect relevant heterogeneity across any known demographic measure that might be used as a criterion for representative samplings. In addition, as previously mentioned, this study is conducted in conjunction with another study examining these orthoptic tests in a target population of young adults; therefore, estimates derived from a similar sample (i.e. young adults) will be applicable to the group we apply it to.

Thus, we will use a convenience sampling of potential participants. Volunteers will be recruited from McGill University and the Montreal area through word-of-mouth and via personal contacts.

# Measures

### Demographic Variables

We will record demographic data relevant to our study in order to appropriately describe the population and explore if these factors modify the test-retest correlations. We will include the year of birth, sex, highest level of education achieved (secondary school, CEGEP, university), the use of corrective glasses for vision problems, and occupation.

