# Study design and methods

The overall study design is a test-retest reliability study of seven different orthoptic tests in healthy participants aged 16 to 35 years. In order to determine if there is clinically useful agreement and consistency between the results when the orthoptic tests are repeated, each participant will be assessed at two time points.

At each time point, participants will be evaluated with seven orthoptic measures:

- (T1) at participant's earliest convenience
- (T2) 1 week following their initial visit

Each of the seven orthoptic measures will be administered to each participant by the same clinician (DT). To minimize the risk that the clinician will remember the scores of any participant, we will set up each testing day so that the clinician sees up to five participants in a random order. At their next and final visit, all the same participants will return to be evaluated, but their order will be altered from their initial visit. To further decrease the likelihood of clinician memory affecting the responses, a research assistant will record the test results as reported verbally by the clinician. After a participant has completed his/her two visits, a research assistant will enter the data into the proprietary software which will provide the clinician with their official "chart" that is required as part of good management practice.

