### Analysis plan

The main objective is to evaluate the agreement and consistency between measurements of the visual system taken at two different times to determine the test-retest reliability of the orthoptic measures. If the tests are perfectly reliable, we would expect the value of the first test to equal the value of the second test for each participant across the range of values for all individuals. The difference between the first and second test for each participant is called the within-group (each participant represents a group) variance. The difference across individuals is the between-group variance. We will assess reliability using the intra-class coefficient (ICC) which measures the between-group variance divided by the total variance (sum of between- and within-group variance). If the within-group variance is 0 (first and second measures are identical), then the ICC = 1 (between-group variance / (between-group variance + 0)). In addition to the ICC, limits of agreement will be estimated using the paired data and illustrated via Bland-Altman plots [18].

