### Sample Size Calculation

Sample size planning is based on the ICC which is our primary outcome. We consider a clinically relevant value in the study population to be ICC  $\ge 0.75$ . Because the measured ICC will vary from sample to sample, we need to consider how precise the estimate of ICC should be. We consider the lower bound of clinical acceptability to be an ICC of 0.5 [19]. Therefore, if the true ICC is 0.75, our estimate precision (95% confidence interval width / 2) must be within 0.25 of the true estimate (0.75 to 0.5). If we include 20 participants, the precision of our ICC estimate

will be  $\pm 0.20$  [19]. This will be slightly more precise than is required, but allows us to account for some potentially missing data or minor technical problems that may occur during the study.

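### The demographic exploration targets test-retest correlations, which mix spread between people with retest error; it should describe retest error by factor instead

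*Combined protocol and SAP*

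**What the plan says.** Under Demographic Variables, the protocol collects background data to describe the sample and to "explore if these factors modify the test-retest correlations". The factors are listed there: "We will include the year of birth, sex, highest level of education achieved (secondary school, CEGEP, university", followed by use of corrective glasses and occupation. That makes five factors. Year of birth is continuous and education has three levels.

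The Analysis plan section does not return to this exploration. It gives no model, contrast, grouping, test or rule of interpretation for it. Its only reliability coefficient is the "intra-class coefficient (ICC) which measures the between-group variance divided by the total variance". It also plans limits of agreement and Bland-Altman plots from the paired data, but does not mention doing so by factor.

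The Sample Size Calculation section sizes the study for one overall ICC: "If we include 20 participants, the precision of our ICC estimate" is put at ±0.20. The sampling rationale under Exclusion Criteria says "we do not expect relevant heterogeneity across any known demographic measure" that might serve as a criterion for representative sampling.

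**The concern.** The ICC is a ratio. Its numerator is how much people differ from each other; retest error enters only through the denominator. If glasses wearers, say, are a more varied group than non-wearers, their ICC is higher even when the test is exactly as repeatable in both. Conversely, if one group has both more spread and more error, the two can cancel and the ICCs agree although the test is noisier in that group.

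What a later user needs to know about a demographic factor is mostly whether the test is noisier in some people. The tests are to be used in a larger project on concussion symptoms, where the spread between people need not match that of healthy volunteers. A modifier finding stated only as a correlation would not tell that project whether measurement error differs.

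**Working it through.** **Inputs from the protocol.** N = 20, true ICC r = 0.75, 95% confidence, required half-width 0.25 and stated half-width 0.20 (Sample Size Calculation); k = 2 measurements per person (Study design and methods); ICC = B/(B + W), with B the between-person and W the within-person variance (Analysis plan).

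**Assumptions, not in the protocol.** A 10 v 10 split, with 14 v 6 as a second case; a two-sided 5% comparison, unadjusted; normal scores.

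**Step 1: the plan's own figure.** The usual precision formula for an ICC with full interval width w is n = 8z²(1 − r)²(1 + (k − 1)r)² / [k(k − 1)w²] + 1. With z = 1.96, r = 0.75, k = 2 and w = 0.40, this is 8 × 3.8415 × 0.0625 × 3.0625 / (2 × 0.16) + 1 = 19.4, so 20. At n = 20 the half-width is 0.197. The stated ±0.20 reproduces.

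**Step 2: the same formula in a subgroup.** At n = 10 the half-width is 0.29. The exact F interval around 0.75 is 0.30 to 0.93. With no true difference, the difference between two ICCs from 10 v 10 has a 95% range of −0.49 to +0.49.

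**Step 3: the ICC under changes in spread and error.** Take W = 1 and B = 3, so that the ICC is 3/4 = 0.75.
- Between-person SD halved, same error: B = 0.75, ICC = 0.75/1.75 = 0.43.
- Between-person SD doubled, same error: B = 12, ICC = 12/13 = 0.92.
- Error SD doubled, same spread: W = 4, ICC = 3/7 = 0.43.
- Both doubled: B = 12, W = 4, ICC = 12/16 = 0.75.

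The first and third cases give the same ICC for opposite reasons. The fourth hides a doubled error completely.

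**Step 4: how often a comparison would flag a difference.** Simulation, 10 v 10, with group 1 at ICC 0.75. The ICCs are compared on the Fisher z scale with variance 1/(n − 1.5). Retest error is compared by an F test on the centred variance of d = T2 − T1, with 9 and 9 degrees of freedom.

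| Group 2 differs by | Comparing ICCs | Comparing variance of d |
|---|---|---|
| nothing | 5% | 5% |
| between-person SD × 0.5 | 18% | 5% |
| between-person SD × 2 | 26% | 5% |
| error SD × 1.5 | 10% | 20% |
| error SD × 2 | 18% | 50% |
| error SD × 3 | 31% | 88% |
| both SDs × 2 | 5% | 50% |

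With 14 v 6 the pattern is the same: comparing ICCs flags a two-fold spread difference in 16% to 20% of runs. The F test finds a doubled error SD in 31% to 49%, depending on which group has the larger error.

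**Step 5: limits of the alternative.** At 10 v 10 the 95% CI for a ratio of error SDs is the estimate divided and multiplied by √F(0.975; 9, 9) = 2.0. Power of 80% needs an SD ratio of about 2.7; detecting a ratio of 1.5 with 80% power needs about 50 per group. With heavier-tailed errors (t, 5 df) the F test's false-positive rate is 9.8%. A Brown-Forsythe test holds 3.5%, but its power for a doubled SD is 27%.

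**Step 6: why the differences must be centred.** The mean of d²/2 is a within-person variance only if the mean shift is zero. With a shift of 1 SD of d in both groups (SD as in the lower-error group), its power for a doubled error SD drops from 54% to 25%. With that shift in one group only and equal random error, it flags 17%. The centred variance stays at about 50% and 5%.

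**The case against.** The strongest reply is that the plan contains one exploratory clause and no subgroup test. The split, the test and the 5% level above are mine. That is right, so the percentages illustrate size and do not describe a stated procedure. For the same reason, a reader should not infer a predicted count of false positives from the number of factors and tests: the plan commits to no significance testing here. What stands is that the clause names a correlation as its target, and the dependence on spread follows from the plan's own definition without any simulation.

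A second reply is that an ICC which differs because of spread is a real difference in relative reliability, as the plan defines it. This also stands. Subgroup ICCs may be shown; they mislead only when read as differences in measurement error. Barring them, or dropping factors from the exploration, would be a matter of preference.

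Third, the planned limits of agreement already measure retest error and mean shift. They do, but as stated only overall. Showing them by factor would be most of the fix.

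A reader might also infer that the exploration ignores a systematic shift between visits. That would hold for a Pearson coefficient, which the plan never names. Under the Analysis plan's definition, the difference between a participant's two tests counts as within-person variance, so a shift lowers the ICC.

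**Conclusion.** The point holds as a minor one. The named target cannot separate a noisier test from a more uniform group of people. Under the stated assumptions, comparing ICCs flags a pure two-fold spread difference in 18% to 26% of studies, where comparing within-person variance keeps 5%. It finds a doubled error SD in about 18% against about 50%, and in 5% if spread doubles as well.

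Three stronger readings are not supported. First, a reader might infer that comparing within-person error cures the weakness of a sample of 20. It removes the dependence on spread and has more power, but still misses about half of two-fold and 80% of 1.5-fold differences in error SD. Second, a reader might infer that a null result is meant to vindicate convenience sampling. The sampling rationale states an expectation of no relevant heterogeneity but does not propose that inference. Third, the primary objective, one overall ICC per measure, and its sample size are untouched.

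**What to change.** In Demographic Variables, replace the correlation as the target with retest error, and add a short paragraph to the Analysis plan:

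- For each categorical factor, report by group the mean of T2 − T1, the SD of the differences about the group mean (or the limits of agreement) with a 95% CI, and the between-person SD beside any subgroup ICC.
- For year of birth, regress the absolute centred difference on year of birth instead of splitting the sample.
- Treat the ordinal saccade score separately, for example by the share of participants with the same category at both visits.
- State that the exploration is descriptive, that 20 participants can show only large differences, and that absence of a difference is not evidence of no modification.

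No extra participants, visits or measurements are needed, since the paired differences are already formed for the limits of agreement. The cost is a little more analysis and a more modest claim. Variance ratios are sensitive to non-normal errors, so any formal comparison should carry a robust check, which has less power.

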### Orthoptic Measures of the Visual System

Most clinicians understand that eye function can be tested for acuity, field of vision and convergence using standard tests available at any clinician's office. However, these tests can only detect gross deficiencies. Optometrists have access to specialized equipment to detect more subtle visual deficiencies. The field of orthoptics uses even more advanced equipment to measure very small deviations in several domains of the visual system. All orthotic measures will be conducted by a single clinician. A detailed description of the 7 orthoptic measures follows:

### Gross stereoscopic acuity: (range 0-15 arc seconds)

Our binocular vision allows us to see in three dimensions (3D), or more simply, to see depth. In this test, seated participants wearing 3D glasses are shown images. Inability to see depth or 3D will cause images to appear as points instead of objects. The objects are presented in different stages, with each stage requiring them to discriminate different levels of depth perception. The test is scored in optical units, with a range of 0 to 15 arcseconds. The maximum score corresponds to the level where the last object was identified.

# Convergence measured by "motor punctum proximum": (cm)

When an object is moving towards our eyes, they symmetrically converge in order to maintain focus. However, there is a point at which our eyes no longer symmetrically converge (point of convergence or motor punctum proximum). This test measures the distance (cm) between the bridge of the nose and point of convergence in seated participants as an object is moved closer to the head.

#### *Binocular fusion with convergence: (diopters, prism convergence units)*

This test measures how well someone can adapt to challenges in focusing light on the retina. There are two almost identical tests. One test occurs with an object placed at 3m from the seated participant, and the other with an object at 30cm from the seated participant. Light from an image is passed through a prism. This is analogous to moving the image further away from the body. In response, the eyes must diverge (separate) to focus on the object, just as they would if the image actually moved away from the body. Different prisms are used to create increasing challenges. The score for these tests is simply the maximum amount of prism convergence (dioptres, noted on the prism, as one would note diopters on eye glasses) that the seated participant can accommodate at 3m and at 30cm.

#### *Saccadic movements or oculomotor capacity: (Score = bad, medium, good)*

A light appears on the screen and the participant move their eyes to fix on the object. While they eyes adjust, they will temporarily cover small distances until they achieve a fixed focus. These are called saccadic movements. Lights appear and disappear, in different locations on the screen, at a rate of 100 per minute, lasting 2 minutes. The test result is scored by the evaluator based on a global impression over the entire 2 minutes, with 3 separate sub scores on an ordinal scale for quality (bad, medium, good), for synchronization (bad, medium, good) and saccadic correction (many corrections, few corrections, no corrections). The three sub scores are combined into an overall score according to our industry partner's (Apexk) proprietary algorithm.

#### Anatomic oculomotor deviation: (diopters, prism convergence units)

This test measures the eyes' natural deviation (heterophoria) and also allows the detection of strabismus. In strabismus, anatomic deviation is evident and the person's dominant eye is looking at you, but the "lazy/deviated" eye is not. In heterophoria anatomic deviation is not visible to the naked eye and the deviation has to be triggered by covering in sequence, one eye at a time, to trigger the deviation. There are two identical tests: one occurs with an object placed at 3m from the seated participant (far vision), and the other with an object at 30cm from the seated participant (near vision). In this test, seated participants focus on an object. These movements can be seen by the orthoptist. The orthoptist covers/uncovers eyes to trigger movements and uses a prism to cancel the movement. The prism that achieves this cancellation is considered the score for this test, with one score for the object placed at 3m and another score for the object placed at 30cm. Participants with strabismus are excluded in our study because strabismus is a contra-indication to post-concussion visual training, which is part of our larger study and thus, patients with strabismus do not represent our target population.

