#### Convergence fusional proximum: (diopters, prism convergence units)

This test is similar to (2) above. When an object is moving closer to our head, the eyes symmetrically converge. When the object is moved beyond the participant's ability to converge, the participant will start to see two images (double vision). This test measures the distance between the bridge of the nose and point where double vision (cm) occurs in seated participants as an object is moved closer.

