#### Binocular fusion with divergence: (diopters, prism convergence units)

This is the same test as (3), except that the prisms diverge the light and the participant has to converge their eyes to maintain focus. The score for these tests is simply the maximum amount of prism divergence (diopters, noted on the prism, as one would note diopters on glasses) that the seated participant can accommodate at 3m, and at 30cm.

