### Data collection and analysis

At the point of recruitment, a research assistant will describe what is needed of the participant in the study and then the participant will provide informed consent. At the first visit, a research assistant will collect demographic information of each participant. At each visit, the seven orthoptic tests will be administered to the participant by the single clinician (DT) as outlined above. Once each participant has completed their two testing periods, the data will be entered into the patient file by a research assistant. Following, the data will be exported into a comma-separated file for analysis using statistical software. The clinician conducting the orthoptic tests will not be involved in the data extraction or analysis phases.

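### Does the eye-deviation test need a written rule for coding the direction of the cancelling prism, and does the diopter unit on the fusional proximum heading matter?

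*Combined protocol and SAP*

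**What the plan says.** In the combined protocol and SAP, the section *Anatomic oculomotor deviation* has the orthoptist cover and uncover the eyes and use a prism to cancel the resulting movement. The scoring sentence is "The prism that achieves this cancellation is considered the score for this test", with one score per distance. Its heading gives the unit as diopters (prism convergence units).

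The same unit label heads three other tests:

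- *Binocular fusion with convergence*, where "The score for these tests is simply the maximum amount of prism convergence" the participant can accommodate.
- *Binocular fusion with divergence*, headed "Binocular fusion with divergence: (diopters, prism convergence units", although "The score for these tests is simply the maximum amount of prism divergence".
- *Convergence fusional proximum*, headed "Convergence fusional proximum: (diopters, prism convergence units", although "This test measures the distance between the bridge of the nose and point where double vision (cm) occurs".

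On data handling, *Study design and methods* says that "a research assistant will record the test results as reported verbally by the clinician". The results then go into proprietary software and the patient file, and from there to a comma-separated export. *Data collection and analysis* adds: "The clinician conducting the orthoptic tests will not be involved in the data extraction or analysis phases". *Analysis plan* applies an ICC (between-participant variance over total variance) and Bland-Altman limits to the paired scores.

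**The concern.** An eye can deviate inwards or outwards, and prisms of the same strength but opposite direction cancel the two. Both statistics need one number per participant per visit, and no section says how direction enters that number. The unit label does not help, because it also heads tests that score prism convergence, prism divergence and a distance. In the two fusion tests the text fixes the direction; in the deviation test it does not.

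The data path sharpens the worry. The clinician who sees the direction speaks the result aloud, someone else writes it down, and the clinician is kept out of extraction and analysis. If only a diopter value reached the export, a deviation that changed direction between visits would look like agreement, and the direction might not be recoverable.

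The fusional proximum heading looks like a plain contradiction: diopters in the title, centimetres in the text.

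**Working it through.** **1. The plan's own figure.** *Sample Size Calculation* gives ±0.20 for 20 participants and a true ICC of 0.75, with two measurements each. The large-sample half-width is

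1.96 × √[2(1−r)²(1+(k−1)r)² / (k(k−1)(n−1))], with r = 0.75, k = 2, n = 20

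= 1.96 × √[2 × 0.0625 × 3.0625 / 38] = 1.96 × 0.1004 = 0.197.

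The stated ±0.20 reproduces. It depends on neither the sign rule nor the unit, so neither point touches the sample size.

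**2. If direction is kept.** Calling one direction positive and the other negative gives a signed score. Which is called positive does not matter: reversing every sign leaves all variances, and so the ICC, unchanged, and only mirrors the limits of agreement. The single question is whether direction is retained.

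**3. If only the magnitude were analysed: the limits.** For any two readings x and y, the difference between |x| and |y| is never larger in size than the difference between x and y. With no systematic shift between visits, the limits can therefore only narrow or stay the same.

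**4. If only the magnitude were analysed: the ICC, normal model.** Assumptions, none taken from the documents except the target 0.75: normal signed readings, total variance 1, between-participant variance 0.75, within-participant variance 0.25. The signed limits are ±1.96 × √(2 × 0.25) = ±1.386 SD. With mean deviation zero there is a closed form:

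unsigned ICC = (2/π)(r·asin r + √(1−r²) − 1) / (1 − 2/π) = 0.521 at r = 0.75.

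The total variance of the magnitudes is 1 − 2/π = 0.363. The within part is 0.363 × (1 − 0.521) = 0.174 (from 0.25), and the between part is 0.363 × 0.521 = 0.189 (from 0.75). Both fall, the between part by more. Hence a lower ICC alongside narrower limits: 1.96 × √(2 × 0.174) = 1.156.

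Simulation gives the other means:

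| Mean deviation (SD from zero) | Unsigned ICC | Limits (±SD) | Narrower than 1.386 by |
|---|---|---|---|
| 0 | 0.52 | 1.156 | 17% |
| 0.5 | 0.59 | 1.187 | 14% |
| 1 | 0.68 | 1.252 | 10% |
| 1.5 | 0.72 | 1.318 | 5% |
| 2 | 0.74 | 1.360 | 2% |

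At 3 SD the ICC is 0.75 and the limits ±1.38: no practical difference.

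**5. A different shape reverses the ICC effect.** Let 85% of participants have true deviations near zero (SD 0.2) and 15% larger ones (SD 3), all centred on zero, with error SD 0.68. The between variance is 0.85 × 0.2² + 0.15 × 3² = 0.034 + 1.35 = 1.384, and the within variance is 0.68² = 0.462. The signed ICC is 1.384 / 1.846 = 0.75, as before. By simulation the unsigned ICC is 0.81, above the signed value. With 10% or 25% in the wider group (and the error rescaled to hold the signed ICC at 0.75) it is 0.82 or 0.78. So no general direction of bias in the ICC can be claimed.

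**6. The heading.** The text of *Convergence fusional proximum* describes a distance in centimetres and likens the test to test (2), the motor punctum proximum, which is itself headed in cm. Two statements against one heading settle the unit. The ICC is free of scale, and the limits come out in whatever unit was recorded, which is centimetres.

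**The case for a change.** The best case for acting is that the rule is missing, would cost one line and a column on the recording sheet, and may be impossible to supply afterwards, because the one person who sees the direction takes no part in the analysis. Under the normal model centred on zero, a test that truly meets the 0.75 target would appear close to the protocol's 0.5 floor, while its limits would look better than they are.

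The first part stands: no coding rule is written, and the unit label does not supply one. The inference to harm does not. The score is defined as the prism, not as its strength, and the two fusion sections already distinguish prisms by direction, so a record that names the prism names its direction too. One clinician tests everyone at both visits, which favours a consistent report. Between the spoken result and the export lie proprietary software and the patient file, whose fields the documents do not show; they may well carry direction, and nothing indicates that they lose it.

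The fall to 0.52 is also one point on a range that depends wholly on an assumed distribution, and the range includes no effect and an effect the other way. Nor can it be turned into a chance of failing a 0.5 threshold: *Sample Size Calculation* uses 0.5 to set the required precision and states no rule that the lower confidence limit must exceed it.

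**Conclusion.** No change to the plan follows. The direction rule is unstated detail that the clinician's record and an analyst would ordinarily fill by signing the prism value, and then both planned statistics are exactly as intended. A distortion needs an extra step that the documents nowhere describe, namely reducing the prism to its magnitude. In that case the limits of agreement would be too narrow (2% to 17% under the normal model with mean 0 to 2 SD from zero). The ICC could be lower (0.52 to 0.74 under the same model) or higher (about 0.8 with a few large deviations), always against an assumed signed value of 0.75. The documents give no distribution from which to choose among these.

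The diopter unit on the fusional proximum heading is a clerical slip. The test's own text and its sister test both give centimetres, and no ICC, limit or sample size depends on the heading.
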